1.1. Synopsis

Protocol Title: A Phase 1b, Two-Part, Open-Label, Fixed-Sequence, Safety, Tolerability and Drug-Drug Interaction Study Between Single Dose Erenumab or Galcanezumab and Multiple Dose Ubrogепant in Participants with Migraine

Protocol Number: 3110-108-002

Brief Title: Drug-Drug Interaction Study of Ubrogепant with Erenumab or Galcanezumab

Study Phase: 1b

Study Rationale:

Ubrogепant is a novel, oral calcitonin gene-related peptide (CGRP) receptor antagonist, currently seeking approval for the acute treatment of migraine. Migraine patients with episodic or chronic migraine are likely to be taking Aimovig[®] (erenumab) or Emgality[®] (galcanezumab) subcutaneously (SC) for the prevention of migraines. There is a high likelihood that physicians could prescribe ubrogепant for the acute treatment of breakthrough migraines in patients already taking migraine preventives. Ubrogепant is extensively metabolized in the liver by cytochrome P450 (CYP)3A4, while erenumab and galcanezumab are not metabolized by CYP enzymes. Although a significant metabolic interaction is not expected when ubrogепant and erenumab or ubrogепant and galcanezumab are co-administered, this study will evaluate the potential for a pharmacokinetic (PK) interaction and provide safety and tolerability information when ubrogепant and erenumab or ubrogепant and galcanezumab are co-administered.

Objectives and Endpoints:

Objectives	Endpoints

Primary To evaluate the effect of single dose erenumab or galcanezumab on the PK of multiple dose ubrogепant in participants with migraine
	
Primary Area under the plasma concentration versus time curve from time 0 to time t (AUC_{0-t}) and from time 0 to infinity ($AUC_{0-\infty}$), and maximum plasma drug concentration (C_{max}) of ubrogепant when ubrogепant and erenumab or ubrogепant and galcanezumab are administered together and when ubrogепant is administered alone

Objectives	Endpoints

Secondary To evaluate secondary PK parameters of ubrogепant following administration of ubrogепant and erenumab or ubrogепant and galcanezumab and when ubrogепant is administered alone
 
To evaluate the safety and tolerability profiles when ubrogепant and erenumab or ubrogепant and galcanezumab are administered in combination and when administered alone in participants with a history of 2 or more migraine attacks per month
 
[REDACTED]
	
Secondary Time of maximum plasma drug concentration (T_{max}), terminal elimination rate constant (λ_z), terminal elimination half-life ($T_{1/2}$), apparent total body clearance of drug from plasma after extravascular administration (CL/F), and apparent volume of distribution during the terminal phase after extravascular administration (V_z/F) of ubrogепant when ubrogепant and erenumab or ubrogепant and galcanezumab are co-administered and when ubrogепant is administered alone
 
Changes from baseline in vital signs, clinical laboratory measurements, physical examinations, and electrocardiograms (ECGs)
 
Incidence of adverse events (AEs) including severity and causality of AEs, as well as AEs leading to discontinuation
 
[REDACTED]

Overall Study Design:

This study will be a Phase 1b, 2-part, multi-center, open-label, fixed-sequence drug interaction study in 40 male and female participants who have been diagnosed with migraine for at least 1 year and are aged 18 through 50 years. In Part 1, 20 participants will receive a single oral dose of 100 mg ubrogепant alone (Study Intervention A) on Day 1, a single SC injection of 140 mg erenumab alone (Study Intervention B) on Day 8, followed by once daily oral doses of 100 mg ubrogепant on Days 12 through 15 (Study Intervention D) under fasted conditions. Similarly, in Part 2, a separate cohort of 20 participants will receive a single oral dose of 100 mg ubrogепant alone (Study intervention A) on Day 1, 2 consecutive SC injections of 120 mg galcanezumab alone (Study intervention C) on Day 8, followed by once daily oral doses of 100 mg ubrogепant on Days 12 through 15 (Study Intervention D) under fasted conditions.

If all doses are well tolerated, the duration of participation in the study will be 46 ± 3 days (Day -1 through the safety Follow-up visit on Day 45), not including the Screening Visit.

- Duration:
 - Screening: Up to 21 days (Day -21 to Day -1)
 - Intervention Period: Up to a total of 17 days (Day -1 to Day 16)
 - Follow-up period: 30 (± 3) days after the last dose
- PK and Biomarker Sampling

In Part 1 and Part 2, PK and biomarker blood samples for the analysis of ubrogепant and CGRP concentrations will be collected at 0 hour (predose), 0.5, 1, 1.5, 2, 3, 4, 5, 6, 8, 12, 14, and 24 hours postdose on Days 1 and 12.

- 
- Safety Measurements

The safety and tolerability profiles when ubrogепant and erenumab or ubrogепant and galcanezumab are co-administered and when each study intervention is administered alone in participants with migraine will be evaluated by clinical assessment of AEs, physical examinations, safety 12-lead ECGs, standard laboratory safety tests (hematology, serum chemistry, and urinalysis), and by measurements of vital signs at specified time points after each study intervention.

Number of Participants:

A total of 40 participants will be enrolled in the study; 20 participants in Part 1 and a separate cohort of 20 participants in Part 2. Part 1 and Part 2 will enroll in parallel. 

 Participants who prematurely discontinue from the study may be replaced at the discretion of the sponsor.

[figure not shown]
Number of Sites: Up to 3 sites in the United States

[figure not shown]
Intervention Groups and Study Duration:

- | | |
|-----------------------|--|
| Study Intervention A: | Single oral 100-mg dose of ubrogепant tablet on Day 1 |
| Study Intervention B: | Single subcutaneous injection of 140-mg erenumab on Day 8 |
| Study Intervention C: | Two consecutive subcutaneous injections of 120-mg galcanezumab on Day 8 |
| Study Intervention D: | Repeated once daily oral doses of 100-mg ubrogепant on Days 12, 13, 14, and 15 |

If all doses are well tolerated, the duration of participation in the study will be 46 ± 3 days (Day -1 through the safety Follow-up Visit on Day 45), not including the Screening Visit.

Data Monitoring Committee: No

2. Introduction

Migraine affects 18% of women and 6% of men in the United States with a peak prevalence occurring between the ages of 25 to 55 years. Approximately one third of those with migraine have 3 or more migraines per month, and over half report severe impairment or the need for bed rest during an attack (Lipton et al, 2007). In the United States, work loss due to migraine is estimated to cost ~ \$13 billion annually (Hu et al, 1999). Prevalence is similar in Europe, with migraine affecting 17.6% of women and 8% of men (Stovner and Andree, 2010). The Global Burden of Disease Study 2010 (Vos et al, 2012) estimated the global prevalence of migraine to be 14.7%, making it the third most common disease in the world in both males and females. Migraine was ranked seventh highest among specific causes of disability globally (Steiner 2013).

Calcitonin gene-related peptide (CGRP) is a neuropeptide implicated in the pathophysiology of migraine. CGRP levels in the cranial venous outflow (ie, external jugular vein) are increased during a migraine attack (Goadsby and Edvinsson, 1993) and exogenously administered CGRP has been shown to trigger migraine-like headache in migraineurs. The majority (80 to 90%) of trigeminal A δ fibers that innervate the dura contain CGRP, suggesting that these fibers may be involved in sterile neurogenic inflammation and migraine pain transmission. Furthermore, the CGRP receptor is present on human meningeal and cerebral blood vessels. These observations suggest that activation of the trigeminovascular system, with release of CGRP, may play a key role in migraine pathogenesis and that inhibition of CGRP function may yield a novel therapeutic approach to treating migraine.

This study will evaluate the safety, tolerability, and PK of ubrogепant, a CGRP antagonist, when administered to participants with migraine receiving erenumab or galcanezumab.

2.1. Study Rationale

Ubrogепant is a novel, oral CGRP receptor antagonist, currently seeking approval for the acute treatment of migraine. Migraine patients with episodic or chronic migraine are likely to be taking Aimovig (erenumab) or Emgality (galcanezumab) subcutaneously (SC) for the prevention of migraines. There is a high likelihood that physicians could prescribe ubrogепant for the acute treatment of breakthrough migraines in patients already taking migraine preventives. Ubrogепant is extensively metabolized in the liver by cytochrome P450 (CYP)3A4, while erenumab and galcanezumab are not metabolized by CYP enzymes. Although a significant metabolic interaction is not expected when ubrogепant and erenumab or ubrogепant and galcanezumab are co-administered, this study will evaluate the potential for a PK interaction and provide safety and tolerability information when ubrogепant and erenumab or ubrogепant and galcanezumab are co-administered.

2.2. Background

Ubrogепant

Ubrogепant, a novel oral CGRP receptor antagonist, that is chemically distinct from both telcagepant and MK-3207, is being developed for the acute treatment of migraine. Current standard of care for the acute treatment of migraines includes triptans, NSAIDs, and ergots. Ubrogепant has completed Phase 3 evaluation for the acute treatment of migraine.

Preclinical and clinical studies conducted to date for ubrogепant have shown no evidence of hepatotoxicity. The toxicity studies conducted to date have demonstrated considerable safety margins over the projected efficacious clinical exposure. For the highest anticipated dose used in clinical studies of 100 mg with potential redosing in the same day (AUC 4.4 $\mu\text{M}\cdot\text{hr}$ for a total dose of 200 mg), the safety margins are 3.5- and 74-fold over the rat NOAEL and monkey NOEL exposures, respectively. The nonclinical toxicity profile of ubrogепant via the oral route of administration supports the continuation of dosing via the oral route in appropriately designed clinical trials. The findings from the developmental toxicology studies in rats and rabbits and a fertility study in rats support inclusion of women of childbearing potential (WOCBP) in clinical trials in compliance with the study protocol and applicable regulatory guidelines.

In Phase 1 studies, single doses of 1 to 400 mg ubrogепant and multiple doses of ubrogепant up to 400 mg once daily (QD) for 10 consecutive days and 150 mg QD for 28 consecutive days have been evaluated. Ubrogепant was generally safe and well tolerated in these studies. In the multiple dose safety and tolerability studies evaluating hepatic effects of 150 mg QD for 28 days and high frequency, intermittent dosing of 100 mg (2 days ubrogепant followed by 2 days placebo) for 56 days, no signs of drug-induced liver injury (DILI) were observed based on a systematic measurement of serum ALT and aspartate aminotransferase (AST). The most frequently reported clinical AEs in these Phase 1 studies include nasopharyngitis, headache, and nausea. Adverse events have generally been transient and mild to moderate in intensity. Dose-proportional PK was noted in the dose range of 1 to 400 mg. Ubrogепant is rapidly absorbed with maximum plasma concentrations achieved in 0.5-1.5 hours. Ubrogепant is metabolized to an inactive metabolite almost exclusively by CYP3A4 with subsequent glucuronidation. Ubrogепant has a short terminal elimination half-life ($T_{1/2}$) of 5 to 7 hours with no accumulation after QD repeated dosing.

A Phase 2b clinical study was conducted, which compared 1-, 10-, 25-, 50-, and 100-mg doses of ubrogепant to placebo in the acute treatment of migraine. Overall, all the ubrogепant doses tested were well tolerated and the adverse event profile of all ubrogепant doses did not differ significantly from placebo. For the primary efficacy endpoint of pain freedom at 2 hours, ubrogепant doses of 1 and 10 mg did not differ from placebo, but doses of 25, 50, and 100 mg were better than placebo. For the primary efficacy endpoint of pain relief at 2 hours none of the ubrogепant doses differed from placebo, probably due to a high placebo response rate.

Further efficacy and safety of ubrogепant were established in 2 randomized, double-blind, placebo-controlled, single-attack, Phase 3 studies (UBR-MD-01 and UBR-MD-02). The results from these studies demonstrated that both ubrogепant 50 mg and 100 mg are superior to placebo in the acute treatment of migraine based on the coprimary efficacy endpoints (pain freedom and

absence of the most bothersome migraine-associated symptom at 2 hours after the initial dose of investigational product). Study UBR-MD-02 demonstrated that ubrogepant 25 mg was superior to placebo for the coprimary endpoint pain freedom at 2 hours after the initial dose; however, statistical significance was not achieved for the coprimary endpoint absence of the most bothersome migraine-associated symptom at 2 hours after the initial dose. The efficacy in each study was supported by the prospectively defined secondary and additional endpoints. A long-term safety extension study, UBR-MD-04, was conducted and supported the safety of ubrogepant evidenced in the 2 pivotal studies.

Additional information and a detailed description of the chemistry, pharmacology, toxicology, efficacy, and safety of ubrogepant can be found in the ubrogepant Investigator's Brochure, (Edition 6, 2019). Rationale for dose selection is described in Section 4.3.

Erenumab

Erenumab-aooe (Aimovig[®]) is a human immunoglobulin G2 (IgG2) monoclonal antibody (MAB) that has high affinity binding to the CGRP receptor and antagonizes CGRP receptor function. Erenumab is indicated for the preventive treatment of migraine in adults. Erenumab is produced using recombinant DNA technology in Chinese hamster ovary (CHO) cells. It is composed of 2 heavy chains, each containing 456 amino acids, and 2 light chains of the lambda subclass, each containing 216 amino acids, with an approximate molecular weight of 150 kDa.

Erenumab exhibits non-linear kinetics as a result of binding to the CGRP receptor. Less than 2-fold accumulation was observed in trough serum concentrations (C_{\min}) for episodic and chronic migraine patients following SC administration of 70 mg once monthly and 140 mg once monthly doses. Serum trough concentrations approached steady state by 3 months of dosing. The effective half-life of erenumab is 28 days. Median peak serum concentrations were attained in approximately 6 days, and estimated absolute bioavailability was 82%. Two elimination phases were observed for erenumab. At low concentrations, the elimination is predominantly through saturable binding to target (CGRP receptor), while at higher concentrations the elimination of erenumab is largely through a non-specific, non-saturable proteolytic pathway. Erenumab is not metabolized by CYP enzymes; therefore, interactions with concomitant medications that are substrates, inducers, or inhibitors of CYP enzymes are unlikely.

Additional information for erenumab can be found in the [Aimovig[®] USPI](#).

Galcanezumab

Galcanezumab-gnlm (Emgality[®]) is a humanized immunoglobulin G4 (IgG4) MAB that binds to CGRP ligand and blocks its binding to the receptor. Galcanezumab is produced in CHO cells by recombinant DNA technology. Galcanezumab is composed of 2 identical immunoglobulin kappa light chains and 2 identical immunoglobulin gamma heavy chains and has an overall molecular weight of approximately 147 kDa.

Galcanezumab exhibits linear PK and exposure increases proportionally with doses between 1 and 600 mg. A loading dose of 240 mg achieved the serum galcanezumab steady-state concentration after the first dose. The time to maximum concentration is 5 days, and the elimination half-life is 27 days. Following a SC injection of galcanezumab, the time to maximum

concentration was about 5 days. Galcanezumab is expected to be degraded into small peptides and amino acids via catabolic pathways in the same manner as endogenous IgG. Galcanezumab is not metabolized by CYP enzymes; therefore, interactions with concomitant medications that are substrates, inducers, or inhibitors of CYP enzymes are unlikely.

Additional information for galcanezumab can be found in the [Emgality[®] USPI](#).

2.3. Benefit/Risk Assessment

Detailed information about the known and expected benefits and risks and reasonably expected adverse events of ubrogепant may be found in the ubrogепant Investigator's Brochure. Based on the observed nonclinical and clinical safety profile of ubrogепant, evaluation of ubrogепant in large Phase 3 trials was supported and these trials are currently completed with a potentially favorable risk/benefit. Since ubrogепant is an investigational product currently being considered for approval by the US FDA, the benefit/risk assessment of the product has not yet been completed by the FDA.

3. Objectives and Endpoints

Objectives	Endpoints

Primary To evaluate the effect of single dose erenumab or galcanezumab on the PK of multiple dose ubrogepant in participants with migraine
	
Primary Area under the plasma concentration versus time curve from time 0 to time t (AUC_{0-t}) and from time 0 to infinity ($AUC_{0-\infty}$), and maximum plasma drug concentration (C_{max}) of ubrogepant when ubrogepant and erenumab or ubrogepant and galcanezumab are administered together and when ubrogepant is administered alone

Secondary To evaluate secondary PK parameters of ubrogepant following administration of ubrogepant and erenumab or ubrogepant and galcanezumab and when ubrogepant is administered alone
	
Secondary Time of maximum plasma drug concentration (T_{max}), terminal elimination rate constant (λ_z), terminal elimination half-life ($T_{1/2}$), apparent total body clearance of drug from plasma after extravascular administration (CL/F), and apparent volume of distribution during the terminal phase after extravascular administration (V_z/F) of ubrogepant when ubrogepant and erenumab or ubrogepant and galcanezumab are co-administered and when ubrogepant is administered alone

To evaluate the safety and tolerability profiles when ubrogepant and erenumab or ubrogepant and galcanezumab are administered in combination and when administered alone in participants with a history of 2 or more migraine attacks per month
	
Changes from baseline in vital signs, clinical laboratory measurements, physical examinations, and ECGs Incidence of AEs including severity and causality of AEs, as well as AEs leading to discontinuation

4. Study Design

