4.1. Overall Design

This study will be a Phase 1b, 2-part, multi-center, open-label, fixed-sequence drug interaction study in 40 male and female participants who have been diagnosed with migraine for at least 1 year and are aged 18 through 50 years. In Part 1, 20 participants will receive a single oral dose of 100 mg ubrogепant alone (Study Intervention A) on Day 1, a single SC injection of 140 mg erenumab alone (Study Intervention B) on Day 8, followed by once daily oral doses of 100 mg ubrogепant on Days 12 through 15 (Study Intervention D) under fasted conditions. Similarly, in Part 2, a separate cohort of 20 participants will receive a single oral dose of 100 mg ubrogепant alone (Study intervention A) on Day 1, 2 consecutive SC injections of 120 mg galcanezumab alone (Study intervention C) on Day 8, followed by once daily oral doses of 100 mg ubrogепant on Days 12 through 15 (Study Intervention D) under fasted conditions.

If all doses are well tolerated, the duration of participation in the study will be 46 ± 3 days (Day -1 through the safety Follow-up Visit on Day 45), not including the Screening Visit.

- Duration:
 - Screening: Up to 21 days (Day -21 to Day -1)
 - Intervention Period: Up to a total of 17 days (Day -1 to Day 16)
 - Follow-up period: 30 (± 3) days after the last dose

- PK and Biomarker Sampling

In Part 1 and Part 2, PK blood samples for the analysis of ubrogепant and CGRP concentrations will be collected at 0 hour (predose), 0.5, 1, 1.5, 2, 3, 4, 5, 6, 8, 12, 14, and 24 hours postdose on Days 1 and 12.

[REDACTED]

- Safety Measurements

The safety and tolerability profiles when ubrogепant and erenumab or ubrogепant and galcanezumab are co-administered and when each study intervention is administered alone in participants with migraine will be evaluated by clinical assessment of AEs, physical examinations, safety 12-lead ECGs, standard laboratory safety tests (hematology, serum chemistry, and urinalysis), and by measurements of vital signs at specified time points after each study intervention.

- Number of Participants

A total of 40 participants at up to 3 sites in the United States will be enrolled in the study; 20 participants in Part 1 and a separate cohort of 20 participants in Part 2. Part 1 and Part 2 will enroll in parallel. [REDACTED]

██████████. Participants who prematurely discontinue from the study may be replaced at the discretion of the sponsor.

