6.1. Study Intervention(s) Administered

- Study Intervention A: Single oral 100-mg dose of ubrogapant tablet on Day 1
- Study Intervention B: Single SC injection of 140-mg erenumab on Day 8
- Study Intervention C: Two consecutive SC injections of 120-mg galcanezumab on Day 8
- Study Intervention D: Repeated once daily oral doses of 100-mg ubrogapant on Days 12, 13, 14, and 15

Migraine participants will be randomized to either Part 1 or 2 and will receive study interventions in a fixed sequence. Parts 1 and 2 could be conducted in parallel. In Part 1, 20 participants will receive a single oral dose of 100 mg ubrogapant alone (Study Intervention A) on Day 1, a single SC injection of 140 mg erenumab alone (Study Intervention B) on Day 8, followed by once daily oral doses of 100 mg ubrogapant on Days 12 through 15 (Study Intervention D) under fasted conditions. Similarly, in Part 2, a separate cohort of 20 participants will receive a single oral dose of 100 mg ubrogapant alone (Study Intervention A) on Day 1, 2 consecutive SC injection of 120 mg galcanezumab alone (Study Intervention C) on Day 8, followed by once daily oral doses of 100 mg ubrogapant on Days 12 through 15 (Study Intervention D) under fasted conditions. There will be a 7-day washout period between the administration of Study Intervention A and Study Intervention B (Part 1) or Study Intervention A and Study Intervention C (Part 2) and an 11-day washout period between ubrogapant doses.

Table 6-1 Study Interventions

Study Intervention Name	Ubrogепant (Intervention A)	Ubrogепant (Intervention D)	Aimovig (Erenumab) (Intervention B)	Emgality (galcanezumab) (Intervention C)
Dose Formulation	Tablet	Tablet	Solution for injection	Solution for injection
Identity of Formulation	100 mg ubrogепant	100 mg ubrogепant	140 mg/mL erenumab aooe	120 mg/mL galcanezumab gnlm
Device Configuration	NA	NA	Single-dose prefilled SureClick autoinjector [REDACTED] or single-dose prefilled syringe [REDACTED]	Single-dose prefilled pen [REDACTED] or single-dose prefilled syringe [REDACTED]
Route of Administration	Oral	Oral	Subcutaneous injection	Subcutaneous injection

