8.5. Pharmacokinetics

8.5.1. Blood PK Sampling Procedure

Starting on Days 1 and 12, PK blood samples to determine ubrogепant plasma concentrations will be collected at 0 hour (predose) and 0.5, 1, 1.5, 2, 3, 4, 5, 6, 8, 12, 14, and 24 hours postdose. These samples may also be used to determine CGRP concentrations.

PK blood samples should be drawn at the nominal times specified above, relative to the dosing time, and the actual time of the blood draw must be recorded in the source documents and eCRFs. Samples taken more than ± 5 minutes from the nominal time will be noted as protocol deviations, and the reason for deviation must be recorded in the source documents and eCRFs. Predose samples must be drawn within 30 minutes of the dosing time.

Study center staff will record the atomic clock times of all blood draws for each participant and will label Vacutainer and polypropylene tubes with a coded label that corresponds to the

participant number and blood draw time. The study center will supply the coded labels. The study center will be responsible for Vacutainer, polypropylene tubes, and all other supplies.

Any changes in the timing or addition of timepoints for any planned study assessments must be documented and approved by the relevant study team member and then archived in the sponsor and site study files but will not constitute a protocol amendment. The IRB will be informed of any safety issues that require alteration of the safety monitoring scheme or amendment of the ICF.

[figure not shown]
A qualified phlebotomist will collect each participant's blood via an indwelling catheter or venipuncture from either arm into prechilled 4-mL Vacutainer tubes containing K₂EDTA as an anticoagulant ([Appendix 9](#)).

[figure not shown]
Blood Volume Collected per Participant

- Total: approximately 194 mL
- PK and biomarker blood samples: 104 mL (26 blood samples, 4 mL each)
- Screening and end-of-study clinical laboratory analysis: 90 mL

Within 30 minutes from the time of the blood draw, blood samples must be centrifuged at no less than 2500g for 10 minutes at approximately 4°C. After centrifugation, the plasma samples will be harvested and transferred into 2 prechilled, coded polypropylene tubes. The samples will then be flash-frozen in a dry ice and alcohol bath (with isopropyl alcohol, ethanol, isopropanol, or methanol) and stored at approximately -20°C.

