9.4.1.2. Statistical Analyses of Pharmacokinetic Data

Details of the statistical analyses of ubrogепant PK data (concentrations and parameters) will be described in the PK analysis plan finalized before database lock.

Descriptive statistics will be provided for all PK parameters of ubrogепant for participants in the Pharmacokinetic PK1 population by study part and by study intervention. PK parameters (C_{max} , AUC_{0-t} , and $AUC_{0-\infty}$) for ubrogепant will be compared using a linear mixed-effects model with study intervention as fixed effect and participant as a random effect.

Statistical analysis will be based on log-transformed values for the C_{max} and AUC parameters of ubrogепant. The 2-sided 90% CI for each study part will be constructed for the ratio of least squares geometric means of C_{max} , AUC_{0-t} , and $AUC_{0-\infty}$ of ubrogепant in combination with CGRP MAB on Day 12 versus ubrogепant alone on Day 1. No effect of co-administration with CGRP MABs on the PK of ubrogепant will be concluded if the 90% CIs for the ratios of ubrogепant PK parameters for test study intervention versus reference study intervention are within the limits of 80% to 125%.

Descriptive statistics will be reported for the plasma concentrations of ubrogепant by study part at each nominal time point for all participants in the Pharmacokinetic PK1 population. [REDACTED]

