### **4 Objectives**

The primary objective of this study is to evaluate the effect of single dose erenumab or galcanezumab on the PK of ubrogepant in participants with migraine. The secondary objectives of the study are to evaluate secondary pharmacokinetic (PK) parameters of ubrogepant following administration of ubrogepant and erenumab, or ubrogepant and galcanezumab, and when ubrogepant is administered alone as well as the safety and tolerability profiles when ubrogepant and erenumab or ubrogepant and galcanezumab are administered in combination and when administered alone in participants with a history of 2 or more migraine attacks per month. [REDACTED]

[REDACTED]

[figure not shown]
[REDACTED]

[figure not shown]

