## **7.2 Statistical Analysis**

Plasma PK parameters ( $C_{max}$ ,  $AUC_{0-t}$ , and  $AUC_{0-\infty}$ ) for ubrogepant will be compared using a linear mixed-effects model with study intervention as fixed effect and participant as a random effect in each part of the study for the PK1 population. Statistical analysis will be based on log-transformed values for the  $C_{max}$  and AUC parameters of ubrogepant. For each study part, the 2-sided 90% CI will be constructed for the ratio of least squares geometric means of  $C_{max}$ ,  $AUC_{0-t}$ , and  $AUC_{0-\infty}$  of ubrogepant in combination with CGRP MAB (Test, Day 12) versus ubrogepant alone (Reference, Day 1). No effect of co-administration with CGRP MABs on the PK of ubrogepant will be concluded if the 90% CIs for the ratios of ubrogepant PK parameters for test study intervention versus reference study intervention are within the limits of 80% to 125%.

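### Does a primary objective on the PK of multiple-dose ubrogepant need plasma profiles that the plan does not collect?

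*Protocol*

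**What the plan says.** The protocol's objective tables (Sections 1.1 and 3) give the primary aim as "To evaluate the effect of single dose erenumab or galcanezumab on the PK of multiple dose" ubrogepant. SAP Section 4 is shorter: the aim is to "evaluate the effect of single dose erenumab or galcanezumab on the PK of" ubrogepant, with no mention of multiple dosing.

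Ubrogepant is given once on Day 1 and then daily on Days 12 to 15. The antibody is given on Day 8. Protocol Section 6.1 describes "an 11-day washout period between" ubrogepant doses. Protocol Section 4.1 schedules plasma samples at "0 hour (predose), 0.5, 1, 1.5, 2, 3, 4, 5, 6, 8, 12, 14, and 24 hours postdose on Days 1 and 12", and Section 8.5.1 gives the total as "PK and biomarker blood samples: 104 mL (26 blood samples, 4 mL each").

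The comparison is named identically in both documents. Protocol Section 9.4.1.2 takes ubrogepant "in combination with CGRP MAB on Day 12 versus" ubrogepant alone on Day 1. SAP Section 7.2 takes ubrogepant "in combination with CGRP MAB (Test, Day 12) versus" ubrogepant alone as the Day 1 reference. In both, no effect is concluded if the 90% confidence intervals lie within 80% to 125%.

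Protocol Section 2.2 reports a half-life "of 5 to 7 hours with no accumulation after QD repeated dosing". Protocol Section 4.2 links the repeated doses to the safety and tolerability of the combination.

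**The concern.** The objective speaks of multiple-dose PK, but both plasma profiles follow a single dose. Day 12 is the first ubrogepant dose after the antibody and comes 11 days after the only previous one. Three of the four co-administered doses have no postdose plasma sample.

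The two documents also word the primary objective differently, and SAP Section 9 records no changes that would explain this. A no-effect conclusion set beside the protocol's objective could be read as a measured repeated-dose result. It would in fact be a first-dose result extended by inference. What would be at stake is the scope of the claim, not the estimate.

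**Working it through.** **1. Is there a third plasma profile?** The protocol lists 13 nominal times (0, 0.5, 1, 1.5, 2, 3, 4, 5, 6, 8, 12, 14 and 24 h) on two days.

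- Samples: 13 × 2 = 26. Volume: 26 × 4 mL = 104 mL. With 90 mL for clinical laboratory tests, 104 + 90 = 194 mL. All three match Protocol Section 8.5.1.
- A third profile would need 13 × 3 = 39 samples and 39 × 4 = 156 mL, or 246 mL in total. There is none.
- SAP Section 5.5.1 adds a 0.25 h time, which gives 14 × 2 = 28 samples and 112 mL, yet it still states 26 and 104 mL. Its figure of 52 samples is 26 for each part, and a participant is in only one part. Neither slip adds a sampling day.

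**2. Is the Day 12 versus Day 1 ratio sound?** The gap is 11 × 24 = 264 h. The residual fraction is 2^(−264/T½).

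| T½ | Half-lives elapsed | Residual fraction |
|---|---|---|
| 5 h | 52.8 | 1.3 × 10⁻¹⁶ |
| 7 h | 37.7 | 4.4 × 10⁻¹² |

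Carry-over is nil, so the ratio compares like with like.

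**3. How far would repeated dosing move exposure?** Assume one-compartment, linear, time-independent kinetics, with k = ln 2 / T½. Accumulation by dose 4 is R = (1 − e^(−4·24k)) / (1 − e^(−24k)).

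| T½ | R at dose 4 |
|---|---|
| 5 h | 1.037 |
| 6 h | 1.067 |
| 7 h | 1.102 |

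This agrees with the protocol's statement that ubrogepant does not accumulate.

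**4. How far would it move the interaction ratio?** R describes exposure, not the ratio of test to reference.

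- *AUC.* Under the same assumptions, AUC over a dosing interval at steady state equals single-dose AUC0-∞; both are dose divided by CL/F. The ratio with and without antibody is therefore the same after one dose as after repeated doses.
- *Cmax.* R cancels if the antibody leaves the half-life unchanged. As an extreme case, suppose the antibody moved the half-life across the whole range, from 5 h to 7 h. The accumulation factors would then differ by 1.102 / 1.037 = 1.06. With volume fixed, that shift would also raise AUC0-∞ by 7 / 5 = 1.40, which fails the 125% limit on Day 12.

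A change in clearance of that size would therefore show in the profile that is measured.

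**5. Does the rest of the plan promise a repeated-dose PK result?** The listed parameters are AUC0-t, AUC0-∞, Cmax, Tmax, λz, T½, CL/F and Vz/F (Protocol Section 9.4.1.1). SAP Section 6.1 lists the same set plus the extrapolated percentage. There is no trough, dosing-interval AUC or accumulation index. The endpoints, sampling, model and decision rule all describe the Day 12 versus Day 1 comparison.

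**The case for a change.** The best argument for a change is that a primary objective should match what is measured and should read the same in both documents. Calling multiple dose the name of the regimen works for the study title. It is weaker for an objective whose subject is the PK of the multiple-dose drug. Protocol Section 4.3 adds to the doubt by calling once-daily dosing adequate for the study's objectives without naming a PK sample that serves them. The correction would be a few words.

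Part of this stands: the wording is loose, and the SAP's version describes the data better. The consequence does not follow. The conclusion rule is already attached to a ratio labelled with its two days, so a reader would have to pass over the endpoints, the sampling schedule and the analysis section to mistake it for a steady-state result. The SAP's objective is shorter than the protocol's, not contrary to it, and SAP Section 5.1 repeats the Day 12 to 15 regimen. Removing the phrase from the objective alone would also leave it at odds with the title, and Protocol Section 10.1.1 sends amendments to the IRB.

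Nor can it be shown that the documents never explain the extension to repeated dosing. Text is blacked out in Protocol Sections 4.2 and 9.4.1.2, and Section 8.5.2 is not in the public text. The count of 26 excludes a third plasma profile, but not an explanation.

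**Conclusion.** No change is needed. The objective and the SAP differ by two words, and the protocol's wording is broader than its plasma sampling. The planned estimate, its confidence interval and its decision rule are correctly specified as Day 12 versus Day 1 and are identical in both documents. Carry-over is below 10⁻¹¹. Predicted accumulation by the fourth dose is 1.04 to 1.10, and its expected effect on the AUC ratio is nil. Different wording would give the same samples, analysis and conclusion.

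This rests on linear, time-independent ubrogepant kinetics, in line with the dose proportionality and lack of accumulation in Protocol Section 2.2. It also assumes that the antibody acts on Days 13 to 15 much as it does on Day 12. That is plausible with antibody half-lives of 27 to 28 days, although the reported peaks at about 5 to 6 days after injection would fall on Days 13 to 14. Rewording the objective would not test either assumption.
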